6.3.4.2. Binary Assessment of Toxicity Relatedness to Study Medications

For the purposes of study reporting, we will use a binary reporting system for documenting relation to study medications. Specifically, any adverse event that is **not related** or **probably not related** to the study medications WILL NOT be reported as treatment related toxicities. Conversely, any adverse event that is **possibly related**, **probably related**, or **definitely related** WILL be reported as treatment related toxicities.

6.3.4.3. Attribution of Relationship to Study Medications

For every adverse event, the Investigator must also attribute whether the adverse event was due to (A) SM-88, (B) methoxsalen, (C) phenytoin, (D) sirolimus, (E) a combination of study medications (specify which), or (F) other causes.

If an Investigator's opinion of probably not or not related to study drug(s) is given, another cause of event must be provided by the Investigator for the adverse event.

6.4. Adverse Event Collection Period

All adverse events reported from the time of the administration of study drug until discontinuation of therapy will be collected, whether elicited or spontaneously reported by the patient. Serious adverse events related to the study or study procedures will be collected from the time the patient signs the study-specific informed consent. All SAEs, regardless of relationship to the study, will be reported from the time of first dose until the End of Treatment visit.

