Lipid Panel (total cholesterol, LDL, HDL, and triglycerides) (within 8 days)	_____
Study Drug Accountability	_____
Dispense SM-88 and MPS	_____
CT c/a/p with IV contrast or MRI or PET/CT (diagnostic CT)	_____
Bone scan (optional, at investigator discretion)	_____
Brain MRI (if history of brain metastases or current suspicious neurologic symptoms)	_____
Tumor Measurements	_____
Cell-free DNA (cfDNA) collection	_____
Study Drug Accountability	_____

Every 8 Weeks After First Response Assessment

(Until CR, PR, or SD confirmed on two consecutive restaging scans)

CT c/a/p with IV contrast or MRI or PET/CT (diagnostic CT)	_____
Bone scan (optional, at investigator discretion)	_____
Brain MRI (if history of brain metastases or current suspicious neurologic symptoms)	_____

Tumor Measurements _____
Lipid Panel (total cholesterol, LDL, HDL, and triglycerides) (within 8 days) _____
Cell-free DNA (cfDNA) collection _____

Every 8-12 Weeks - After Disease Response Confirmed

(If patients achieve a CR, PR, or SD confirmed on two consecutive restaging scans, Response Assessment may transition to every 12 weeks)

CT c/a/p with IV contrast or MRI or PET/CT (diagnostic CT) _____
Bone scan (optional, at investigator discretion) _____
Brain MRI (if history of brain metastases or current suspicious neurologic symptoms) _____
Tumor Measurements _____
Lipid Panel (total cholesterol, LDL, HDL, and triglycerides) (within 8 days) _____
Cell-free DNA (cfDNA) collection _____

Day 1 of Subsequent Cycles

Concomitant Medications _____
Pregnancy Test (within 8 days) _____
Weight _____
Vital Signs _____
Interval History and Physical _____
Performance Status _____
Adverse Event Evaluation _____
CBC with Differential (within 8 days) _____
Serum Chemistries (within 8 days) _____
Study Drug Accountability _____
Dispense SM-88 and MPS _____

End of Treatment (+ 10 days from last dose)

Weight _____
Vital Signs _____
Concomitant Medications _____
Interval History and Physical _____
Performance Status _____
Adverse Events Evaluation _____
CBC with Differential (within 8 days) _____
Serum Chemistries (within 8 days) _____
Lipid Panel (total cholesterol, LDL, HDL, and triglycerides) (within 8 days) _____
Study Drug Accountability _____
CT c/a/p with IV contrast or MRI or PET/CT (diagnostic CT); if not done within 30 days prior to the visit _____
Bone scan (optional, at investigator discretion) _____

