¹¹ End of Treatment visit should occur as soon as possible at the time of progression or discontinuation of treatment, preferably before the subject starts the next therapy, + 10 days from last dose. Imaging and tumor assessments do not need to be performed at this visit if performed within 30 days prior to the visit.

¹² Bone scan at investigator discretion

¹³ Long term follow up assessment (+/- 4 weeks). Patients will be contacted by phone call or e-mail for vital status data collection, adverse events evaluation (if AEs from study have not yet been closed), subsequent anti-breast cancer therapy (systemic therapy, radiation, or surgery), and development of a secondary malignancy.

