6.5. Adverse Event Reporting

In the event of an SAE, whether related to study drugs, study procedures, or even if not directly related to any study intervention, the Investigator will notify the PI, [name], the Multicenter Project Managers, and IRB as required per local IRB policy after being made aware of the serious adverse event. Furthermore, the Investigator will forward all treatment emergent SAE reports regardless of causality, to TYME within 24 hours of completion of the initial report. The institution will forward both initial and follow-up versions of each SAE report.

TYME REPORTING:

The SAE report should comprise a full written summary, detailing relevant aspects of the adverse events in question. Where applicable, information from relevant hospital case records and autopsy reports should be included. Follow-up information should be forwarded to TYME within 24 hours. SAEs brought to the attention of the Investigator at any time after cessation of the study drugs and considered by the Investigator to be related or possibly related to the study drugs must be reported to the study PI, [name], Multicenter Project Manager(s) and to the IRB when they occur, if required by the local IRB policy.

For patients enrolled outside of Georgetown University, serious adverse events will also be reported, and all supporting documentation sent (emailed) to the Multicenter Project Manager(s) and to the study PI, [name], within 24 hours. Emailed records should be sent to the Multicenter Project Manager(s) [REDACTED] and to [name].

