8.4.2.4. Safety Assessments

Overall safety monitoring will be performed throughout the study. The safety of the SM-88 therapy will be assessed by evaluating study drug exposure, adverse events, serious adverse events, and all deaths.

A summarization of the number of days and/or cycles patients were exposed to study drug will be provided. Adverse events (and serious adverse events) will be graded and recorded throughout the study and during the follow-up period according to NCI CTCAE Version 5.0. Toxicities will be characterized in terms of seriousness, causality, toxicity grading, and action taken with regard to trial treatment. The percentage of patients experiencing an adverse event at a given severity, NCI CTCAE toxicity grade, and relationship to study drug will be provided. The number of patient deaths throughout the study will be summarized.

8.4.3. Exploratory Endpoints:

Descriptive statistics will be used to analyze any changes in cell-free DNA (cfDNA) measurement at baseline (pre-treatment on C1D1), during the SM-88 therapy, and at disease progression time points.

Baseline Characteristics

All baseline summary statistics and analyses will be based on characteristics prior to the initiation of study drug. Frequency and percentages for categorical variables, and mean (SD) or median (IQR, interquartile range) for the continuous variables based on the normalization of the data.

9. Correlative Research Management

9.1. cfDNA

Blood sample collection for analysis of cfDNA analysis will be collected at multiple time points: baseline (pre-treatment), C2D1, C3D1, at each additional restaging scan (every 8-12 weeks) and disease progression. cfDNA samples will be banked at Georgetown University, and eventually shipped to Foundation Medicine for analysis.

All specimens will be collected in two (2) 10 mL Streck cell-free DNA collection tubes (DNA BCT catalog # 230470). These vials shall be processed as per the laboratory instructions provided by Foundation Medicine, and categorized and banked at Georgetown as per protocol. Refer to the Lab Manual for more details on collection, processing, and storage instructions.

10. Ethical Considerations

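### Section 6.4 stops collecting non-serious adverse events at discontinuation of therapy, before the End of Treatment visit that is scheduled to look for them

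*Combined protocol and SAP*

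**What the plan says.** Section 6.4 sets the end of collection for adverse events in general: "All adverse events reported from the time of the administration of study drug until discontinuation of therapy will be collected". It then gives serious events a later end: "All SAEs, regardless of relationship to the study, will be reported from the time of first dose until the End of Treatment visit". It also collects study-related serious events from consent.

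Section 6.5 goes further for some serious events. "SAEs brought to the attention of the Investigator at any time after cessation of the study drugs" and judged related or possibly related are to be reported, subject to local IRB policy.

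The End of Treatment visit comes after treatment has stopped. Footnote 11 to Table 3 (section 4.6) wants it as early as possible, "preferably before the subject starts the next therapy, + 10 days from last dose", and the checklist in section 4.5 gives the same 10 days. The checklist, the calendar and section 4.3.12.1 all include an adverse-event assessment at that visit.

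The safety analysis in section 8.4.2.4 says: "Adverse events (and serious adverse events) will be graded and recorded throughout the study and during the follow-up period". From that record, "The percentage of patients experiencing an adverse event at a given severity, NCI CTCAE toxicity grade, and relationship to study drug will be provided". The statistical section of the synopsis repeats both statements.

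**The concern.** One section uses two different end points, so they cannot be read as the same date. A site that follows the general sentence in 6.4 would not record a new non-serious event found at the End of Treatment visit. A site that follows the checklist would. The analysis section describes a record that extends beyond both, and no section defines a treatment-emergent window or says which rule governs.

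Safety and tolerability is a secondary objective, and the percentages by grade and relationship are its main output. At stake is whether they rest on one window at all five sites. The protocol's own definition in 6.3.1 counts events arising from drug withdrawal as adverse events, and laboratory abnormalities can also qualify. The End of Treatment visit includes blood counts, chemistries and lipids. Some of what that visit is designed to find would therefore fall outside 6.4.

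**Working it through.** The plan gives no figure to reproduce here. The check is a comparison of the windows, followed by simple arithmetic on what one patient is worth.

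**1. Who is covered after discontinuation of therapy**

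| Type of event | Discontinuation to End of Treatment visit | After that visit |
|---|---|---|
| Already recorded, still open | Followed (4.3.10, 6.1, 6.3.1) | Followed (4.5, 4.7, Table 3 footnote 13) |
| Serious, any cause | Reported (6.4) | No rule if unrelated |
| Serious, related or possibly related | Reported (6.4) | Reported, subject to local IRB policy (6.5) |
| New and non-serious | Not collected under 6.4; looked for under 4.3.12.1, 4.5 and Table 3 | No provision for new events |

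The conflict is confined to the last row, second column.

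**2. Length of the gap**

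Gap = date of the End of Treatment visit minus date of discontinuation of therapy.

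- Shortest: 0 days, because footnote 11 asks for the visit as soon as possible.
- Longest: about 10 days, if therapy is discontinued on the day of the last dose and the visit takes place 10 days later.
- In between: where dosing was held before the decision to stop (6.8.1 allows up to 28 days), discontinuation comes after the last dose and the gap shrinks, possibly to 0.

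**3. What one missed patient is worth**

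Section 3.6.2.2 puts every patient with at least one dose in the safety set. Section 3.1.2 plans 50 evaluable patients, and stage 1 has 30. The safety set may be larger, because patients not evaluable for response are replaced.

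Change in a reported percentage = 100 / N.

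- N = 50: 100 / 50 = 2.0 percentage points.
- N = 30: 100 / 30 = 3.3 percentage points.

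This applies when the missed event is the patient's only one of that type.

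**4. Illustration, resting on an assumption**

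The documents give no rate of new events after stopping. Let q be an assumed proportion of patients with a new non-serious event in the gap, with N = 50. Expected patients = Nq, and the chance of at least one = 1 − (1 − q)^N.

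| Assumed q | Expected patients | Chance of at least one |
|---|---|---|
| 2% | 1.0 | 64% |
| 5% | 2.5 | 92% |
| 10% | 5.0 | 99% |

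The table shows only that a low rate would be enough to touch the results. It does not estimate the loss.

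**The case against.** The strongest reply is that the protocol as a whole expects these events to be recorded. Section 4.3.12.1 requires an assessment after discontinuation, the checklist and calendar schedule it, section 6.1 has investigators monitor patients throughout the study, and 8.4.2.4 describes recording into follow-up. Against all this stands one sentence in 6.4. Different windows for serious and non-serious events are also not an error in themselves. This reply stands to the extent that loss is not certain. It does not remove the conflict, because 6.4 is the section that defines the collection period.

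A reader might also infer more than the documents support:

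- **That collection ends at the last dose.** Section 6.4 says discontinuation of therapy. With holds of up to 28 days allowed, the two dates can differ, and for such patients the gap may be nil.
- **That events which made a patient stop, or which worsened afterwards, are lost.** Those events began on treatment, so 6.4 collects them, and 4.3.10, 6.1 and 6.3.1 follow them to a conclusion.
- **That the adverse-event table is the only place where patients who stop for toxicity count, because 3.6.2.1 drops them from the response set.** Section 8.4.1 computes the response rate on all patients with at least one cycle, so this rests on one of two conflicting definitions.
- **That the mention of follow-up in 8.4.2.4 must be a third window for new events.** It can be read as follow-up of open events, which 4.7 provides for. The text should say so.

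**Conclusion.** The inconsistency is real and narrow. It concerns new-onset, non-serious adverse events first appearing between discontinuation of therapy and the End of Treatment visit, a gap of 0 to about 10 days per patient. If 6.4 is applied literally they are not collected. If sites differ in which section they follow, they are captured unevenly and the percentages mix two windows.

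The direction is under-reporting. The number of events cannot be derived from the documents. Each patient affected moves a given percentage by 2.0 points at 50 patients or 3.3 at 30. The primary endpoint, the sample size and the reporting of serious events up to the visit are untouched. The correction is worth making because the visit that would supply the data is already in the schedule.

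**What to change.** - **Section 6.4:** collect all adverse events, serious or not, from first dose through the End of Treatment visit. Keep the existing collection of study-related serious events from consent.
- **Section 8.4.2.4 and the matching statistical text in the synopsis:** state that the adverse-event percentages use that window, plus later serious events judged related or possibly related. Say this outright rather than relying on 6.5, which is a reporting duty qualified by local IRB policy.
- **Same two places:** state that after the End of Treatment visit open events are followed to resolution, and that new non-serious events are not collected. This agrees with 4.7 and with footnote 13 to Table 3.

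Both analysis texts must change together, or a new inconsistency is created. The cost is a protocol wording change and slightly more recording at a visit already scheduled. No visit or procedure is added.

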6.5. Adverse Event Reporting

In the event of an SAE, whether related to study drugs, study procedures, or even if not directly related to any study intervention, the Investigator will notify the PI, [name], the Multicenter Project Managers, and IRB as required per local IRB policy after being made aware of the serious adverse event. Furthermore, the Investigator will forward all treatment emergent SAE reports regardless of causality, to TYME within 24 hours of completion of the initial report. The institution will forward both initial and follow-up versions of each SAE report.

TYME REPORTING:

The SAE report should comprise a full written summary, detailing relevant aspects of the adverse events in question. Where applicable, information from relevant hospital case records and autopsy reports should be included. Follow-up information should be forwarded to TYME within 24 hours. SAEs brought to the attention of the Investigator at any time after cessation of the study drugs and considered by the Investigator to be related or possibly related to the study drugs must be reported to the study PI, [name], Multicenter Project Manager(s) and to the IRB when they occur, if required by the local IRB policy.

For patients enrolled outside of Georgetown University, serious adverse events will also be reported, and all supporting documentation sent (emailed) to the Multicenter Project Manager(s) and to the study PI, [name], within 24 hours. Emailed records should be sent to the Multicenter Project Manager(s) [REDACTED] and to [name].

6.6. Reporting Product Quality Complaints for SM-88

Any written, electronic, or oral communication that alleges dissatisfaction related to manufactured clinical drug product with regards to its manufacturing, testing, labeling, packaging, or shipping, must be reported by the

sponsor-Investigator or qualified designee to TYME within 1 working day of first becoming aware of the possible defect. The product and packaging components in question, if available, must be stored in a secure area under specified storage conditions until it is determined whether the product is required to be returned for investigation of the defect. If the product complaint is associated with an SAE, the SAE must be reported separately in accordance with the protocol, and the SAE report should mention the product quality complaint.

6.7. Pregnancy

Pregnancies (and pregnancy outcomes) occurring in a female patient or a female partner of a male patient must be reported to the Institution within 24 hours. Elective abortions without complications should not be considered AEs unless they were therapeutic abortions. Hospitalization for normal delivery of a healthy newborn should not be considered an SAE. Spontaneous abortions should always be reported as SAEs. The Investigator should follow-up with the study patient or the female partner of the study patient until delivery or termination of pregnancy, even if the patient was withdrawn from the clinical study or the clinical study was completed. TYME will be informed of all pregnancy outcomes.

In the event of a positive pregnancy test result, study drugs will be immediately discontinued. The Investigator must report the positive pregnancy test within 24 hours of the site becoming aware of the pregnancy to the IRB and to TYME. For patients enrolled outside of Georgetown University, documentation should be emailed to the Multicenter Project manager(s) at [REDACTED] and to the study PI, [name], within 24 hours.

Patients should also notify the Investigator if it is determined after completion of the study that they become pregnant either during the treatment phase of the study or within 30 days after the treatment period. Information regarding a pregnancy occurrence in a study patient and the outcome of the pregnancy will be collected, and the status of the mother and child should be reported to the IRB and TYME after delivery. Pregnancy in a study patient is not considered an adverse event but does require discontinuation of the patient from the study. However, the medical outcome of a spontaneous abortion, stillbirth, or congenital anomaly is considered a serious adverse event and must be reported to the IRB and TYME within 24 hours of the site becoming aware of the event.

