8. Asymptomatic brain metastases are allowed if the lesions are not considered to need local therapy. Previously treated brain metastases are allowed as long as they are > 4 weeks from local therapy, clinically asymptomatic, and not requiring high-dose corticosteroids. Patients may remain on steroids for CNS disease if they are taking a stable dose that is less than 10mg of prednisone per day, or the equivalent.

9. Must be capable of understanding and complying with parameters as outlined in the protocol and able to sign and date the informed consent, approved by the IRB, prior to the initiation of any screening or study-specific procedures.
10. Life expectancy of more than 3 months.
11. ECOG performance status 0-1 (Appendix A, Table 7).
12. Pregnancy must be ruled out in women of childbearing potential. Serum or urine pregnancy test must be negative within 14 days of treatment start in women of childbearing potential and must be willing to have pregnancy test approximately every 4 weeks. Pregnancy testing does not need to be pursued in patients who are judged to be postmenopausal before enrollment, or who have undergone bilateral oophorectomy, total hysterectomy, or bilateral tubal ligation.
 - a. Patients may be considered postmenopausal in the case that one of the following criteria applies:
 - i. Prior bilateral oophorectomy, OR
 - ii. Age \geq 60 years, OR
 - iii. Age $<$ 60 years with intact uterus and amenorrheic for \geq 12 consecutive months **prior to** chemotherapy and/or endocrine therapy exposure
13. Willingness to utilize adequate contraception if of childbearing potential. Women of childbearing potential must use adequate contraception for the duration of protocol treatment and for at least 6 months after the last treatment with SM-88 used with MPS.
 - a. Adequate contraception is defined as one highly effective form (i.e., abstinence, (fe)male sterilization) OR two effective forms (IUD [non-hormonal preferred], condom with spermicidal foam / gel / film / cream / suppository, occlusive cap with spermicidal foam / gel / film / cream / suppository).
14. Must be able and willing to swallow pills whole and retain oral medication.
15. Adequate hematologic parameters (Patients must be able to meet the following criteria without transfusion or receipt of colony stimulating factors within 2 weeks before obtaining sample):

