3.4.3. Birth Control

Birth control should be used from the signing of the patient consent form and for 3 months following the last dose of SM-88 and/or MPS. Acceptable methods of birth control include:

- Age \geq 60 years
- At least one highly effective form of contraception (i.e., abstinence, (fe)male sterilization/tubal ligation)
- At least two effective forms (IUD [non-hormonal preferred], condom with spermicidal foam / gel / film / cream / suppository, occlusive cap with spermicidal foam / gel / film / cream / suppository).
- Permanent sterilization, defined as hysterectomy, bilateral salpingectomy, bilateral oophorectomy, or bilateral orchidectomy
- Postmenopausal, defined as a female patient $<$ 60 years of age with intact uterus and amenorrhoeic for \geq 12 consecutive months **prior to** chemotherapy and/or endocrine therapy exposure

In addition, men must not conceive a child or donate sperm during SM-88 and/or MPS therapy, and for 6 months after receiving the last dose of study therapy.

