4.3.13. Longitudinal Outcomes Assessment

Patients will be followed after progression until death (or up to 24 months) to assess overall survival, and to monitor for the development of secondary malignancies. Information pertaining to survival and post-treatment therapy will be collected approximately every 24 weeks (Month 6, 12, 18, and 24) beginning after the final visit, for a period up to 24 months.

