4.7. Long-term follow up

After patients complete participation on study, patients will be followed for survival and AE evaluation (if AEs from study have not yet been closed) every 6 months (+/- 4 weeks) until death, lost to follow-up, patient withdrawal of consent, study discontinued by the Sponsor, or 2 years, whichever comes first. These visits may be conducted in-clinic or by remote contact (e.g., telephone or email).

5. Dosages and Dispensation of Drugs

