6.8.3.3. Related to Sirolimus

Increased Susceptibility to Infection and Possible Development of Lymphoma

Increased susceptibility to infection and the possible development of lymphoma and other malignancies, particularly of the skin, may result from immunosuppression. Oversuppression of the immune system can also increase susceptibility to infection, including opportunistic infections such as tuberculosis, fatal infections, and sepsis. Patients receiving the drug should be managed in facilities equipped and staffed with adequate laboratory and supportive medical resources. The physician responsible for maintenance therapy should have complete information requisite for the follow-up of the patient.

Hypersensitivity Reactions

Hypersensitivity reactions, including anaphylactic/anaphylactoid reactions, angioedema, exfoliative dermatitis and hypersensitivity vasculitis, have been associated with the administration of sirolimus. Discontinue and do not re-administer sirolimus if patients exhibit hypersensitivity during the study.

Angioedema

Sirolimus has been associated with the development of angioedema. The concomitant use of sirolimus with other drugs known to cause angioedema, such as angiotensin-converting enzyme (ACE) inhibitors, may increase the risk of developing angioedema. Elevated sirolimus levels (with/without concomitant ACE inhibitors) may also potentiate angioedema. In some cases, the angioedema has resolved upon discontinuation or dose reduction of sirolimus. Since dose reduction of sirolimus is not applicable in this study due to the dose of sirolimus being one 0.5 mg tablet, dosing with sirolimus should be terminated when angioedema occurs.

Fluid Accumulation and Impairment of Wound Healing

There have been reports of impaired or delayed wound healing in patients receiving sirolimus, including lymphocele and wound dehiscence. mTOR inhibitors such as sirolimus have been shown in vitro to inhibit production of certain growth factors that may affect angiogenesis, fibroblast proliferation, and vascular permeability. Lymphocele, a known surgical complication of renal transplantation, occurred significantly more often in a dose-related fashion in patients treated with sirolimus. Appropriate measures should be considered to minimize such complications. Patients with a body mass index greater than 30 may be at increased risk of abnormal wound healing based on data from the medical literature.

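### Section 6.7 asks patients to notify a pregnancy only up to 30 days after treatment, which is shorter than every contraception period in the protocol; separately, four follow-up passages disagree on what is collected

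*Combined protocol and SAP*

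**What the plan says.** **Pregnancy.** Section 6.7 opens with a duty to report pregnancies, and their outcomes, in a female patient or a male patient's female partner within 24 hours. It gives that duty no end date. A later paragraph adds an instruction to patients: they should also tell the investigator if it emerges after the study that "they become pregnant either during the treatment phase of the study or within 30 days after the treatment period".

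The contraception rules run longer. Inclusion criterion 13 in Section 3.2 requires women of childbearing potential to use "adequate contraception for the duration of protocol treatment and for at least 6 months after the last treatment with SM-88 used with MPS", and Appendix A repeats the 6 months. Section 3.4.3 gives a general period of 3 months after the last dose and adds that "men must not conceive a child or donate sperm during SM-88 and/or MPS therapy, and for 6 months after receiving the last dose".

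**Late follow-up.** Section 4.3.13 follows patients for up to 24 months after the final visit, to assess survival and "to monitor for the development of secondary malignancies", and collects post-treatment therapy. Table 3 footnote 13 lists vital status, adverse events not yet closed, "subsequent anti-breast cancer therapy (systemic therapy, radiation, or surgery), and development of a secondary malignancy". Section 4.7 describes the same 6-monthly contact more narrowly: "patients will be followed for survival and AE evaluation (if AEs from study have not yet been closed"). The follow-up checklist in Section 4.5 likewise has only a patient assessment, open adverse events and vital status.

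On the malignancy risk, Section 6.8.3.3 warns: "Increased susceptibility to infection and the possible development of lymphoma and other malignancies, particularly of the skin, may result from immunosuppression".

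**The concern.** The protocol asks patients to avoid conception for months after the last dose, yet tells them to report a conception only if it falls in the first 30 days. Premenopausal women and men are eligible, and Section 6.8.3.1 says phenytoin may cause fetal harm. If a patient conceives in, say, the third month, the site would learn of it only if the patient volunteered it or it came up by chance. Information on that exposure and its outcome may not be recoverable later.

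The follow-up mismatch is a different problem. A site working from footnote 13 would ask about new malignancy and later therapy at each contact. A site working from the 4.5 checklist would ask about neither. Late data pooled across sites would then mix patients who were asked and had nothing to report with patients who were never asked.

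**Working it through.** No sample size, error rate or event count enters this point, and the plan gives no figure to reproduce. The check compares the lengths of the stated windows and then sets the follow-up passages side by side.

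**1. Notification window against contraception period.** Inputs: 30 days (Section 6.7); 3 months (Section 3.4.3); 6 months (Section 3.2 criterion 13 and Appendix A for women; Section 3.4.3 and Appendix A for men). A month is taken as 30 days, or as 365.25/12 = 30.44 days.

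Share covered = 30 / period; days not covered = period − 30.

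- 3 months: 30/90 = 33.3%, leaving 60 days; 30/91.3 = 32.9%, leaving 61 days.
- 6 months: 30/180 = 16.7%, leaving 150 days; 30/182.6 = 16.4%, leaving 153 days.

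The window is too short whichever contraception period is kept.

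**2. Does anything else ask?** The 4.5 follow-up checklist, Section 4.7 and footnote 13 have no pregnancy item. The End of Treatment list in Section 4.5 and the matching column of Table 3 have no pregnancy test. The 30-day sentence speaks of patients who become pregnant, so it sets no post-treatment window for a male patient's partner.

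**3. Would a question at the first contact be late enough?** The first contact is at 6 months ± 4 weeks. Counted from the last dose, that is 182.6 − 28 = day 155 to 182.6 + 28 = day 211. Counting from an End of Treatment visit up to 10 days after the last dose moves the early limit to at most day 165. Section 4.3.13 instead gives about every 24 weeks, or 24 × 7 = 168 days. All of these can fall before a 6-month period (180 to 183 days) has ended, so the question needs its own timing rule.

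**4. Follow-up content, side by side.**

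- Section 4.3.13: survival, second malignancy, post-treatment therapy.
- Table 3 footnote 13: vital status, open adverse events, later anticancer therapy, second malignancy.
- Section 4.5 follow-up checklist: patient assessment, open adverse events, vital status.
- Section 4.7: survival, open adverse events.

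The first two include second malignancy and later therapy; the last two include neither. With contacts at months 6, 12, 18 and 24, up to four contacts per patient are affected.

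**The case against.** The strongest reply on pregnancy is that Section 6.7 does not stop at 30 days. Its opening duty has no end date and names partners. A known pregnancy is followed to delivery or termination even after withdrawal or study completion, and TYME is told of all outcomes. This stands. A reader might infer that the protocol ignores pregnancies after day 30, or leaves partners out altogether, and the text does not support that. The gap is in what patients are told to notify and what staff ask, not in how a known pregnancy is handled.

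A reader might also take the 3 or 6 months as a stated period of fetal risk. The documents give contraception and no-conception periods and never say how long risk lasts. The percentages compare two windows; they do not estimate missed pregnancies.

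On second malignancy, the version 2.2 change summary records that this item and later therapy were removed from follow-up. So it would be wrong to infer that the 4.5 checklist and Section 4.7 dropped it by oversight; Section 4.3.13 and footnote 13 are more likely the passages left unrevised. The current sections still contradict each other, but asking the sponsor to keep the question would reverse a recorded decision. The warnings also need their context: they come from package inserts, sirolimus is given here at 0.5 mg/day against a labelled 2 to 5 mg/day, and for phenytoin the protocol says causation of lymphoma has not been established. Second malignancy is not a named endpoint, so no planned analysis fails.

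Finally, Section 6.5 covers "SAEs brought to the attention of the Investigator at any time after cessation of the study drugs" when judged related or possibly related. A reader might infer that its closing condition about local IRB policy also makes reports to the study PI and project managers optional. The condition directly follows the mention of the IRB and may qualify only that report. For patients outside Georgetown, the last paragraph of 6.5 requires serious events to go to the PI and project managers within 24 hours without any such condition.

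**Conclusion.** The pregnancy point holds as a mismatch between stated rules. Followed as written, the plan leaves about 60 days (3-month period) to 153 days (6-month period) in which contraception is required but patients are not asked to notify a pregnancy. For partners of male patients no post-treatment notification window is stated. This rests on reading the 30-day sentence as the instruction patients receive, and on a month of 30 to 30.44 days. The number of patients affected cannot be given, because the documents do not say how many will be of childbearing potential.

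The two contraception periods that apply to women, 3 months in Section 3.4.3 and at least 6 in Section 3.2 and Appendix A, also contradict each other and must be reconciled. Nothing here says which is right.

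The follow-up point holds as an inconsistency among four current passages, on second malignancy and on later therapy alike. It does not establish that either item must be collected. No design figure or primary analysis is affected.

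**What to change.** 1. Reconcile Section 3.4.3 with Section 3.2 and Appendix A. The sponsor chooses the period.
2. In Section 6.7, make the patient-notification window no shorter than that period, and name female partners of male patients with their own stated window.
3. Add one pregnancy question, for patients to whom it applies, to an existing follow-up contact held at or after the end of the period. If the period is 6 months, do not let the early side of the ± 4 week allowance apply to that question, or ask it again at the next contact.
4. Make Section 4.3.13, footnote 13, the 4.5 follow-up checklist and Section 4.7 list the same items. Whether to keep second malignancy is the sponsor's decision, weighed against the warnings in Section 6.8.3; later therapy needs the same decision.
5. In Section 6.5, at most clarify that the local IRB policy condition applies to the IRB report only.

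The cost is a wording amendment and a few minutes of site time in a phone or email contact that already takes place. No visit or sample is added.
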